4.2. Extent of Study Drug Exposure and Adherence

Extent of exposure to study drug will be examined by assessing the total duration of exposure to study drug and the level of adherence to the study drug specified in the protocol.

4.2.1. Duration of Exposure to Study Drug

Total duration of exposure to any study drug will be defined as $(\text{last dose date of any study drug} - \text{first dose date of any study drug} + 1)$, regardless of any temporary interruptions in study drug administration and will be expressed in weeks using up to 1 decimal place (eg, 4.5 weeks).

For subjects with a partial last dosing date (ie, month and year of last dose are known), the latest of the dispensing dates of study drug bottles, study drug start dates and end dates, and the imputed last dose date [day imputed as 15] will be used as the final imputed last dose date. If the subject died and the death date is complete (ie, not partial date) and before the imputed last dose date, the complete death date will be used as the imputed last dose date.

If only year is recorded (ie, month and day of last dose are missing), the latest of the dispensing month of study drug bottles, study drug start month, and study drug end month will be used to impute the unknown last dose month. If the subject died and the death date has month and year available and before the imputed last dose month, then the month of death will be used instead. With the month imputed, the aforementioned method will be used to impute the last dose date.

If subjects are continuing on study drug at Week 24 analysis, the earliest of the date of death or data cutoff date for analysis will be used to impute the last dosing date for the calculation of duration of exposure to study drug.

The total duration of exposure to any study drug will be summarized using descriptive statistics and using the number (ie, cumulative counts) and percentage of subjects exposed through the following time periods: Baseline (Day 1), Week 2 (Day 15), Week 4 (Day 29), Week 8 (Day 57), Week 12 (Day 85), Week 14 (Day 99), Week 16 (Day 113), Week 20 (Day 141), Week 24 (Day 169), Week 26 (Day 183), Week 30 (Day 211), Week 36 (Day 253), Week 44 (Day 309) and Week 52 (Day 365). A 7-day window is applied to the last planned on-treatment visit to match the protocol-specified visit window

Summaries will be provided by treatment group for the Safety Analysis Set. No formal statistical testing is planned.

4.2.2. Adherence to Study Drug

Adherence will be calculated separately for filgotinib 200 mg/PTM (tablets), filgotinib 100 mg/PTM (tablets) and adalimumab/PTM (syringes).

The total number of tablets or syringes administered will be summarized using descriptive statistics.

The presumed total number of tablets or syringes administered to a subject will be determined by the data collected on the drug accountability CRF using the following formula:

Total Number of Tablets Administered =

$(\Sigma \text{ No. of Tablets Dispensed}) - (\Sigma \text{ No. of Tablets Returned})$

Total Number of Syringes Administered =

$(\Sigma \text{ No. of Syringes Dispensed}) - (\Sigma \text{ No. of Syringes Returned})$

If a bottle or a packaging kit is dispensed and the bottle or packaging kit is returned empty, then the number of tablets/syringes returned will be entered as zero. If a bottle or a packaging kit is dispensed but not returned (missing), then the number of tablets/syringes returned will be counted as zero.

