5.6. Accountability for Study Drugs

The investigator is responsible for ensuring adequate accountability of all used and unused study drugs. This includes acknowledgement of receipt of each shipment of study drugs (quantity and condition). All used and unused study drugs dispensed to subjects must be returned to the site.

Filgotinib, adalimumab, PTM, and MTX accountability records will be provided to each study site to:

- Record the date received and quantity of study drug
- Record the date, subject number, subject initials, the study drug number dispensed

- Record the date, quantity of used and unused study drugs returned, along with the initials of the person recording the information.
- Dispensing records will include the initials of the person dispensing the study drug or supplies

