3.1.3. Per-Protocol Analysis Set

The Per-Protocol (PP) Analysis Set includes subjects in the FAS who did not have major protocol deviations occurring prior to or on Week 12 that will affect the efficacy analysis, and were compliant (with on-treatment adherence $\geq 80\%$ in the first 12-week period) to study treatment.

Major protocol deviations include the following:

- Violation of at least one of the following key eligibility criteria:
 - 1) Have a diagnosis of RA (2010 ACR/EULAR criteria for RA), and are ACR functional class I-III
 - 2) Have ≥ 6 swollen joints (from swollen joint count based on 66 joints [SJC66]) and ≥ 6 tender joints (from tender joint count based on 68 joints [TJC68]) at both Screening and Day 1 (need not be the same joints)
 - 3) Must meet at least one of the following parameters at Screening:
 - a) ≥ 1 documented joint erosion on radiographs of the hands, wrists or feet by central reading AND a positive result for anti-CCP or RF (based on central laboratory)OR
 - b) ≥ 3 documented erosions on radiographs of the hands, wrists or feet by central reading if both antibodies (ie, RF, anti-CCP) are negative (based on central laboratory)OR
 - c) Serum CRP ≥ 6 mg/L (based on central laboratory)
 - 4) Ongoing treatment with a stable dose of MTX as described in protocol
 - 5) Subjects that have failed prior therapy with a bDMARD are not eligible to participate. Subjects with prior exposure to one bDMARD may be enrolled if there is documented evidence of limited exposure (ie, less than 3 months) to the bDMARD
- Received prohibited concomitant medications
- Background medications were changed in violation of protocol
- Improper study medication administration and unintended medication overdose
- Data were questionable because of significant site quality or compliance issues

Qualifications and identification of the specific major protocol deviations that result in exclusion from the PP Analysis Set will be determined while the study remains blinded, prior to database finalization.

The PP Analysis Set is the secondary analysis set for efficacy analyses on primary and key secondary endpoints at Week 12. Statistical analyses using PP Analysis Set are specified in Section 6.

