4.2.2.1. On-Treatment Adherence

The level of on-treatment adherence to the study drug will be determined by the total amount of study drug administered relative to the total amount of study drug expected to be administered during a subject's actual on-treatment period based on the study drug regimen.

The level of on-treatment adherence will be expressed as a percentage using the following formula:

$$\text{On-Treatment Adherence (\%)} = \left(\frac{\text{Total Amount of Study Drug Administered}}{\text{Study Drug Expected to be Administered on Treatment}} \right) \times 100$$

Note: If calculated adherence is greater than 100%, the result will be set to 100%.

Study drug expected to be administered for filgotinib 200 mg/PTM (tablets) = 1 × total duration of exposure to any study drug (days).

Study drug expected to be administered for filgotinib 100 mg/PTM (tablets) = 1 × total duration of exposure to any study drug (days).

Study drug expected to be administered for adalimumab/PTM (syringes) = ceil[total duration of exposure to any study drug (days) / 14].

For subjects in placebo group who were re-randomized, the switched study drug expected to be administered is defined as:

Study drug expected to be administered for PTM (tablets) = 1 × ((first dose date of filgotinib – 1 – first dose date of any study drug) + 1).

Study drug expected to be administered for filgotinib 100 mg/ filgotinib 200 mg = 1 × ((last dose date of any study drug – first dose date of filgotinib) + 1).

On-treatment adherence will be calculated up to Week 12, up to Week 24 and up to Week 52, respectively.

Descriptive statistics for the level of on-treatment adherence with the number and percentage of subjects belonging to adherence categories (eg, < 80%, ≥ 80 to < 90%, ≥ 90%) will be provided by treatment group for the Safety Analysis Set.

Categorical displays will be presented for the number of subjects who are at least 80% adherent to their study drug regimen (ie, adherence is ≥ 80% for each study drug).

No formal statistical testing is planned.

A by-subject listing of study drug administration and drug accountability will be provided separately by subject ID number (in ascending order) and visit (in chronological order).

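### Adherence scoring treats unreturned drug as taken, so the 80% Per-Protocol condition cannot screen out a subject who returns nothing

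*SAP*

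**What the plan says.** SAP 4.2.2 calculates adherence separately for each tablet strength and for syringes. The presumed number administered "will be determined by the data collected on the drug accountability CRF using the following formula": the total dispensed minus the total returned. Two rules follow for bottles and kits. If "the bottle or packaging kit is returned empty, then the number of tablets/syringes returned will be entered as zero". And: "If a bottle or a packaging kit is dispensed but not returned (missing), then the number of tablets/syringes returned will be counted as zero".

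SAP 4.2.2.1 divides the amount administered by the amount expected. That is one tablet of each strength per day of exposure, or the number of exposure days divided by 14 and rounded up for syringes. Results above 100% are set to 100%. The categorical display there counts a subject as adherent only if every study drug reaches 80%.

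SAP 3.1.3 makes on-treatment adherence of at least 80% in the first 12 weeks a condition of the Per-Protocol set, alongside the absence of major deviations. SAP 6.2.4.1 repeats the primary analysis on that set to gauge the effect of study conduct. SAP 6.3.3.1 repeats every key secondary analysis on it except mTSS.

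On returns, Protocol 5.6 says: "All used and unused study drugs dispensed to subjects must be returned to the site". It also has sites record the quantities of used and unused drug returned.

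**The concern.** A returned empty bottle is some evidence that the contents were taken. A bottle that never comes back is evidence of nothing, yet both receive the same score. The less a subject returns, the higher the computed adherence, so the rule is most generous where the accountability data are poorest.

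The Per-Protocol set exists to show whether the Week 12 results hold among subjects who took their assigned treatment. If subjects with no evidence of dosing are admitted as fully adherent, the set cannot do that for them. This matters for the comparison with adalimumab. In that arm the syringe is the only active investigational product (Protocol 3.3), and the adalimumab response rate enters the 50% retention test directly.

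**Working it through.** The documents give no worked adherence figure to reproduce, so the check applies the SAP rule to simple records.

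**Inputs from the documents.** Expected syringes are days/14 rounded up, and expected tablets are one per day per strength (SAP 4.2.2.1). A bottle holds 30 tablets (Protocol 5.2.2). The threshold is 80% (SAP 3.1.3).

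**Assumptions.** The documents do not state the quantities dispensed by Week 12; Protocol Appendix 2 leaves dispensing to the IWRS manual. I assume 6 syringes and 3 bottles (90 tablets) of each strength. I also read the 80% condition as applying to each product.

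**Rule.** Adherence = min[100%, (dispensed − returned)/expected].

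**Nothing returned.** The score becomes dispensed/expected, with no term for what was taken. The subject passes whenever the supply handed out is at least 80% of the supply expected:

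- 84 days: expected syringes = 84/14 = 6. Score = (6 − 0)/6 = 100%.
- 85 days: 85/14 rounds up to 7. Score = (6 − 0)/7 = 85.7%; with 7 dispensed it is 100%.
- Tablets, 84 days: (90 − 0)/84 = 107%, set to 100%.

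These scores hold if every dose was taken and equally if none was.

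**Part of the supply lost, 84 days:**

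| Tablets taken | Returned | Lost untaken | Score | True adherence |
|---|---|---|---|---|
| 56 | 4 | 30 | (90 − 4)/84 = 102%, set to 100% | 56/84 = 67% |
| 28 | 2 | 60 | (90 − 2)/84 = 105%, set to 100% | 28/84 = 33% |

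Both subjects are below 80% and both are classed as fully adherent.

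**Without the presumption.** A subject who returns nothing has adherence anywhere from 0% to 100%. In the first table row, the accountability data alone support anything from 67% (lost bottle untaken) to 100% (84 tablets taken in all). The threshold lies inside both ranges, so classification has to rest on other information.

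**The case against.** The strongest reply is that this is an openly stated convention with other safeguards around it. The SAP calls the count presumed. Per-Protocol membership also requires no improper administration of study medication (SAP 3.1.3). Non-adherence is given as an example of an important protocol deviation (SAP 4.3), and administration and accountability are listed by subject (SAP 4.2.2.1). The Per-Protocol analyses are sensitivity analyses. Removing everyone with a lost bottle would also misclassify, because some of them took the drug. All of this stands. It limits the consequence and argues against outright exclusion, but none of it changes how the 80% score is computed.

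Nor is there an obvious bias in the non-inferiority test. With equal filgotinib and adalimumab rates, its numerator, π_T − 0.5π_C − 0.5π_P, reduces to 0.5(π_C − π_P). Non-adherence that dilutes both active arms equally shrinks this and makes non-inferiority harder to claim. Only missed dosing concentrated in the adalimumab arm would favour filgotinib, and the documents give no reason to expect that.

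A reader might also infer that the formula subtracts spent syringes, so that a subject who injects 6 and returns all 6 used, as Protocol 5.6 requires, scores (6 − 6)/6 = 0%. The wording "No. of Syringes Returned" does not exclude this, but the documents do not establish it. The empty-kit rule applies to syringes as well as tablets, and the result is labelled as the number administered. Both point to a count of unused contents. The accountability CRF, which would settle the matter, is not among the documents. What remains is a missing word.

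**Conclusion.** The concern holds for unreturned drug. The rule is explicit, and under it a subject who returns nothing scores 85.7% to 100% for syringes and 100% for tablets on the assumed quantities, whatever was taken. True tablet adherence of 33% or 67% can be scored as 100%.

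The effect is confined to the Per-Protocol repeats of the primary and Week 12 key secondary analyses, including non-inferiority. The Full Analysis Set analyses do not use adherence. Direction and size cannot be stated without the share of unreturned kits by arm. The point is worth correcting but does not threaten the main conclusions.

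A reader might extend the criticism to placebo subjects re-randomized at Week 24, on the view that expected placebo tablets stop at the switch although one placebo strength continues. SAP 4.2.2.1 introduces those formulas with "the switched study drug expected to be administered is defined as". This most naturally covers only the strength that changes to active and leaves the other under the full-exposure formula. A Week 24 switch cannot in any case alter membership based on the first 12 weeks.

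**What to change.** For Per-Protocol classification, SAP 4.2.2 should no longer presume that the contents of unreturned bottles or kits were taken. Use the study drug administration record for the periods they covered. Where that record does not establish dosing, report the Per-Protocol results twice, with those subjects included and excluded, and give their number by arm. The presumption can stay for the descriptive adherence tables if it is footnoted.

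State also that the returned-syringe count means unused syringes, and confirm that the CRF field is completed that way.

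The cost is SAP wording and some programming on administration and accountability data that the study already collects. In the version that excludes subjects with unestablished dosing, the Per-Protocol set is slightly smaller and loses some who took the drug but mislaid the container; the paired version shows whether that matters. If the CRF does not separate used from unused syringes, the syringe clarification would also need a check against site accountability records.

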4.2.2.1. On-Treatment Adherence

The level of on-treatment adherence to the study drug will be determined by the total amount of study drug administered relative to the total amount of study drug expected to be administered during a subject's actual on-treatment period based on the study drug regimen.

The level of on-treatment adherence will be expressed as a percentage using the following formula:

$$\text{On-Treatment Adherence (\%)} = \left(\frac{\text{Total Amount of Study Drug Administered}}{\text{Study Drug Expected to be Administered on Treatment}} \right) \times 100$$

Note: If calculated adherence is greater than 100%, the result will be set to 100%.

Study drug expected to be administered for filgotinib 200 mg/PTM (tablets) = 1 × total duration of exposure to any study drug (days).

Study drug expected to be administered for filgotinib 100 mg/PTM (tablets) = 1 × total duration of exposure to any study drug (days).

Study drug expected to be administered for adalimumab/PTM (syringes) = ceil[total duration of exposure to any study drug (days) / 14].

For subjects in placebo group who were re-randomized, the switched study drug expected to be administered is defined as:

Study drug expected to be administered for PTM (tablets) = 1 × ((first dose date of filgotinib – 1 – first dose date of any study drug) + 1).

Study drug expected to be administered for filgotinib 100 mg/ filgotinib 200 mg = 1 × ((last dose date of any study drug – first dose date of filgotinib) + 1).

On-treatment adherence will be calculated up to Week 12, up to Week 24 and up to Week 52, respectively.

Descriptive statistics for the level of on-treatment adherence with the number and percentage of subjects belonging to adherence categories (eg, < 80%, ≥ 80 to < 90%, ≥ 90%) will be provided by treatment group for the Safety Analysis Set.

Categorical displays will be presented for the number of subjects who are at least 80% adherent to their study drug regimen (ie, adherence is ≥ 80% for each study drug).

No formal statistical testing is planned.

A by-subject listing of study drug administration and drug accountability will be provided separately by subject ID number (in ascending order) and visit (in chronological order).

4.3. Protocol Deviations

Subjects who did not meet the eligibility criteria for study entry, but enrolled in the study will be summarized regardless of whether they were exempted by the sponsor or not. The summary will present the number and percentage of subjects who did not meet at least 1 eligibility criterion and the number of subjects who did not meet specific criteria by treatment group based on the All Randomized Analysis Set. A by-subject listing will be provided for those subjects who did not meet at least 1 eligibility (inclusion or exclusion) criterion. The listing will present the eligibility criterion (or criteria if more than 1 deviation) that subjects did not meet and related comments, if collected.

Protocol deviations occurring after subjects entered the study are documented during routine monitoring. The number and percentage of subjects with important protocol deviations by deviation reason (eg, nonadherence to study drug, violation of select inclusion/exclusion criteria) will be summarized by treatment group for the All Randomized Analysis Set. A by-subject listing will be provided for those subjects with important protocol deviation.

5. BASELINE CHARACTERISTICS

5.1. Demographics and Other Baseline Characteristics

Subject demographic and other baseline characteristics variables will be summarized by treatment group and overall using descriptive statistics for continuous variables, and using number and percentage of subjects for categorical variables. The summary of demographic and other baseline characteristics data will be provided for the Safety Analysis Set for the following:

- Age (on the first dose date of any study drug)
- Age group (< 65 years, ≥ 65 years)
- Sex at birth (male, female)
- Race
- Ethnicity (Hispanic or Latino, not Hispanic or Latino)
- Geographic region and country
- Weight (kg)
- Height (cm)
- Body mass index (BMI; in kg/m²)
- Smoking status

A by-subject demographic and other baseline characteristics listing, including the informed consent date, will be provided by subject ID number in ascending order.

5.2. Baseline Disease Characteristics

Baseline disease characteristics include:

- Duration of RA from diagnosis (years)

Calculated as ((first dose date) – (date of initial diagnosis) + 1 day) / 365.25. If the date of initial diagnosis is incomplete, then the following rules will be applied:

— missing day: use the first of the month

— missing month: use January

- Presence of RF (Yes/No)

- Presence of anti-CCP Ab (Yes/No)
- Presence of both RF and anti-CCP Ab (Yes/No)
- Prior exposure to bDMARDs (Yes/No)
- Concurrent oral corticosteroids use on the first dosing date (Yes/No): n (%)
 - Oral corticosteroids dose, mg/day, expressed as prednisone-equivalent dose
- Concurrent MTX use on the first dosing date (Yes/No): n (%)
 - Dose of MTX, mg/week
- Concurrent anti-malarials use on the first dosing date (Yes/No)
- Swollen joint count based on 66 joints (SJC66)
- Tender joint count based on 68 joints (TJC68)
- Swollen joint count based on 28 joints (SJC28)
- Tender joint count based on 28 joints (TJC28)
- HAQ-DI total score
- DAS28(CRP)
- SF-36 physical component summary (PCS) score
- SF-36 mental component summary (MCS) score
- FACIT-Fatigue
- Subject's pain assessment (by visual analog scale [VAS] in mm)
- Subject's global assessment of disease activity [SGA] (by VAS in mm)
- Physician's global assessment [PGA] (by VAS in mm)
- Simplified Disease Activity Index (SDAI)
- Clinical Disease Activity Index (CDAI)
- hsCRP (mg/L)

- hsCRP \geq 6 mg/L (Yes/No)
- mTSS
 - Erosion score
 - Joint space narrowing (JSN) score
- Subject with erosion defined as erosion score $>$ 0 (Yes/No)

A list of anti-malarials is provided in [Appendix 1](#). The baseline disease characteristics will be summarized by treatment group and overall using descriptive statistics for continuous variables and using number and percentage of subjects for categorical variables. The summary of baseline disease characteristics will be provided for the Safety Analysis Set.

A by-subject listing of baseline disease characteristics will be provided by subject ID number in ascending order.

5.3. Medical History

Medical history collected at screening will be coded using the Medical Dictionary for Regulatory Activities (MedDRA) 21.0.

Medical history will be summarized by system organ class (SOC), preferred term (PT), treatment group, and overall. Subjects who report 2 or more medical history items that are coded to the same SOC and/or PT will be counted only once by the unique coded term in the summary.

In addition, numbers and percentages of subjects who have any first degree relatives that had experienced myocardial infarction or stroke before the age of 50 years, experienced myocardial infarction or stroke before the age of 50 years, or have diabetes (type I or II) will be summarized.

The summary will be provided for the Safety Analysis Set. No formal statistical testing is planned.

A by-subject listing of medical history will be provided by subject ID number.

